2.2 Objective

The primary objective of the proposed study is to determine the correlation between baseline mechanical pain threshold (MPT) and analgesic response (% pain reduction) after 4-weeks of treatment with pregabalin vs. placebo in patients with painful peripheral neuropathy induced by oxaliplatin, paclitaxel, and/or docetaxel.

The additional aims of the study are:

1. To investigate whether treatment with pregabalin results in better pain relief compared with placebo in patients with painful CIPN.
2. To identify additional phenotypic predictors of response to pregabalin in CIPN by performing comprehensive baseline somatosensory phenotyping.

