2.4.2 Pre-Study Period

At the screening visit, after obtaining signed informed consent, we will collect patient demographic data including details on cancer type and status, chemotherapy regimen(s) and cumulative doses, history of chronic pain, concomitant diseases and medication, and duration of painful CIPN. A blood sample for CMP will be obtained for determining serum creatinine concentration and liver transaminases (ALT and AST). If subject's lab tests results are available within the past 30 days, we will utilize these without the need of obtaining new renal and hepatic function tests. In addition, the patients will complete the following questionnaires: Brief Pain Inventory (BPI), Neuropathic Pain Symptom Inventory (NPSI), and Depression Anxiety and Positive Outlook Scale (DAPOS). Average and maximum daily pain intensity in the past week will be recorded as baseline pain intensity measure.

The subjects' extremities will be mapped for spontaneous pain, and response to the following sensory stimulation: cold (20°C Thermal Roller, Somedic), warm (40°C Thermal Roller, Somedic), pinprick (# 5.88 Semmes-Weinstein monofilament, 60mN target force, North Coast) and brush (SenseLab 0.5 brush, Somedic) (Finnerup, Sorensen et al. 2007). The probability of neuropathic pain will be graded as possible, probable, or definite according to Treede et al. criteria (Treede, Jensen et al. 2008). The results of sensory mapping will provide the information for the criterion on presence of any objectively tested positive or negative neurological signs in the painful territory. Photographs of the mapped extremities will be taken (in a way not to include any part of the subjects' face or other identifying information), for accurate reproduction of areas of sensory disturbance.

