2.4.3 Study Period

[figure not shown]
The cross-over study design and the treatment plan are illustrated in Figure 1. Pregabalin (or matching placebo) will be administered for four weeks in each period. The target dose will be increased from 75mg BID to 300mg BID within 7 days (per schedule in Fig. 1), and continued for an additional 22 days.

In case of any grade 2 adverse events (Common Terminology Criteria for Adverse Events – CTCAE version 4.0), the dose will be reduced to the last dose prior to dose increase (i.e. to 150mg BID from 300mg BID; to 75mg BID from 150mg BID). If the adverse effect diminishes to \leq Grade 1, one attempt to dose escalate will be allowed after 3 additional days. If the dose escalation is not tolerated (i.e. recurrent grade 2 adverse event), the treatment will be continued at the previous (lower) dose until day 28. Any CTCAE \geq grade 3 will trigger subject withdrawal from the study.

At the end of treatment sequence, the dose will be tapered over 3 days (e.g., 150mg BID for 2 days, then 75 mg BID for 1 additional day) followed by 10 days of study drug-free washout (end of week 6). In subjects with CrCL 30-60 mL/min, the target (maximum) dose will be 300mg/day. In these subjects the dose will be tapered over 3 days of 75mg BID dosing. If subject's highest tolerable maintenance dose was 75mg BID, the taper schedule will be 75mg QD over 3 days.

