The subjects will return on day 28 ± 2 days [prior to washout period] for Visit 2 to turn in the 4 questionnaires which were completed on day 28 (week 4a), sensory mapping, PK blood sample and a blood sample for renal and hepatic function tests will be obtained. After the washout period (end of week 6), the subjects will return to Washington University Medical Center for Visit 3, prior to second treatment sequence. The subjects will undergo QST and CPM procedures (Fig. 1), and complete the appropriate questionnaires (SPI, NPSI, BPI, DAPOS). Thereafter, the second 4-week treatment sequence will be scheduled for weeks 7-10, according to the same titration schedule as sequence 1. Three day dose tapering-down will be practiced at the end of second treatment sequence in the same manner as was performed for the first treatment. The subjects will return for the final assessment visit [Visit 4] approximately 3 days after end of week 10 (end of 3-day taper). Safety and efficacy data, a PK blood sample and a blood sample for renal and hepatic function tests will be obtained, turn in 4 questionnaires which were completed on day 28 (week 4b), sensory mapping, and the optional skin biopsy in subjects who agreed, will be obtained at Visit 4.

Figure 1.

Legend: BPI – brief pain inventory; NPSI – neuropathic pain symptom inventory; DAPOS – depression, anxiety and positive outlook scale; SPI – sleep problem index; QST – quantitative sensory testing; CPM – conditioned pain modulation. Tx – treatment.

Rescue Analgesia

Study subjects will be allowed to take oral acetaminophen (paracetamol) as rescue analgesic at a dose of 1 gram up to 4 times/day. FDA-approved 500mg acetaminophen tablets will be purchased and provided by the investigators. If the patient has been receiving PRN short-acting opioids (with or without acetaminophen) for non-CIPN pain, up to 4 daily doses will be allowed during the study, with daily recording of analgesic consumption. The total amount of acetaminophen (from opioid-acetaminophen combination and PRN acetaminophen alone) will not exceed 4 grams/day. In subjects with liver disease (AST or ALT increased, but less than 3 times the upper normal level), the total daily dose of acetaminophen will be limited to 2 grams. Based on these considerations, each patient will receive individual written instructions regarding PRN analgesic use, and will be required to report it appropriately.

Outcomes Assessment:

Clinical Efficacy

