Patients will complete an electronic diary with daily report of their average and maximum daily pain intensity, recorded every evening before bedtime. The percentage of pain reduction for primary outcome will be assessed from the difference between baseline average pain intensity and the average pain intensity of last 5 days of treatment (day 24-28), on 0-10 NRS.

Secondary efficacy outcomes will include: 1) The difference between baseline maximum pain intensity and the maximum pain intensity of the last 5 days of treatment, on 0-10 NRS; 2) The proportion of patients achieving 50% or more pain relief with pregabalin vs. placebo treatment; 3) Difference in Pain Severity and Pain Interference scales of the BPI, assessed at baseline and day 28 of treatment. The daily use of rescue analgesia (oral acetaminophen) will also be recorded.

Table 1. Data assessment schedule

Required Assessments	Screening and Enrollment Baseline Visit	Week 1a	Week 2a	Week 3a	Week 4a	End of Treatment A (Day 28 +/- 2)	Wash-out	Study crossover visit	Week 1b	Week 2b	Week 3b	Week 4b	End of Study Visit (Day 30 +/- 3)
Study visits	Visit1 (a/b)*					Visit2		Visit3					Visit 4
Informed consent	✓												
Pregnancy (urine Hbhcg) test for women	✓												
Comprehensive Metabolic Panel (CMP) blood test**	✓					✓							✓
Inclusion/exclusion criteria	✓												
Randomization	✓												
Demographic data collection	✓												
Sensory Mapping	✓					✓		✓					✓
BPI questionnaire	✓				✓			✓				✓	
NPSI questionnaire	✓				✓			✓				✓	
DAPOS questionnaire	✓				✓			✓				✓	
SPI questionnaire	✓				✓			✓				✓	
QST	✓							✓					
CPM	✓							✓					
Dispense study drug	✓							✓					
Pain intensity 0-10 NRS	✓	daily	daily	daily	daily			✓	daily	daily	daily	daily	✓
Adverse Event assessment		daily	daily	daily	daily				daily	daily	daily	daily	✓
Telephone communication		weekly	weekly	weekly	weekly				weekly	weekly	weekly	weekly	
Blinding questionnaire***		✓											
Pill count								✓					✓
Blood sample (PK)						✓							✓
Skin biopsy (optional)													✓

*Visit 1 may be conducted over 2 visits to complete all assessments if required for subject tolerability or convenience

** A blood sample for CMP will not be obtained if recent (<30 days) results are available.

*** Blinding questionnaire to be administered via EMA device on Day 5 of study drug treatment

Subject Blinding Perception

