2.4.7 Statistical Methods

The primary outcome is the comparison of slopes of the two correlations: baseline MPT vs % pain reduction with pregabalin, and baseline MPT vs % pain reduction with placebo. Percent pain reduction will be assessed from the difference in average pain intensity at baseline and the average daily pain intensity on days 24-28 of each treatment phase, obtained from the patient diaries. The two slopes will be compared using t-test. Significant difference between slopes will indicate that baseline MPT correlates with pregabalin response (vs. placebo response) in painful CIPN, regardless of differences in average pain response between pregabalin and placebo.

As secondary analyses, we will compare mean absolute pain reduction with pregabalin to absolute pain reduction to placebo (both for average daily pain and maximum daily pain), using paired t-test, given normal data distribution. If normal distribution is not obtained, we will use Wilcoxon signed ranked test. In addition, we will perform Fisher exact test to compare the proportion of patients with 50% or more reduction in average pain intensity from baseline with pregabalin vs. placebo. Number needed to treat (NNT) will be calculated from this proportion of responders to pregabalin and placebo. These secondary analyses are aimed at detecting group differences in response to pregabalin vs. placebo.

In exploratory analysis, we will examine the correlations between the various demographical and QST variables (WDT, CDT, HPT, CPT, WSI, TS, CPM) and pain reduction with pregabalin vs placebo, for generating hypotheses for additional predictors of response to pregabalin in CIPN. We will also perform exploratory multiple regression analysis to evaluate how various QST factors perform in combination as treatment response predictors.

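### Response in both periods is measured from the Visit 1 pain score, with no period term and no role for the off-drug Visit 3 score, so drift between periods stays in the error, without biasing the treatment contrast

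*Combined protocol and SAP*

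**What the plan says.** Section 2.4.2 defines baseline pain at the screening visit: "Average and maximum daily pain intensity in the past week will be recorded as baseline pain intensity measure". Section 2.4.7 then forms the outcome for both phases by comparing "average pain intensity at baseline and the average daily pain intensity on days 24-28 of each treatment phase, obtained from the patient diaries". Its reference to each phase attaches to days 24-28; baseline appears once, unqualified, and no other section defines a second one.

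Section 2.4.3 brings patients back after a 3-day taper and 10 drug-free days "for Visit 3, prior to second treatment sequence". At that visit Table 1 ticks the row "Pain intensity 0-10 NRS", along with the four questionnaires, QST and CPM. Neither the text nor the table says whether this pain score is a past-week average or a single rating, and Table 1 shows no diary entries during washout.

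The primary test in 2.4.7 is a t-test of two slopes (percent reduction on baseline MPT, for pregabalin and for placebo). The secondary test is a paired t-test on absolute reductions, followed by a Fisher exact test and NNT for 50% responders. Sections 2.4.7 to 2.4.9 mention no period or sequence effect and do not use the Visit 3 pain score.

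**The concern.** For whichever treatment comes second, the reduction runs from Visit 1 to the end of week 10, across the other treatment and the washout. Change that happened before the second treatment began is part of that patient's period-2 value. Two things are at stake.

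- **Precision.** A general shift between periods, and each patient's own drift, stay in the residual of both the slope comparison and the mean difference. Section 2.4.8 requires 27 patients and plans for 35 × 0.8 = 28 completers, so there is little slack.
- **Meaning of period-2 response.** Take a patient at 6 at Visit 1 and 4 at Visit 3. Measured from Visit 1, that is already (6 − 4)/6 = 33% before the first period-2 dose. One further point, to 3, makes a 50% responder; measured from Visit 3, two further points are needed, to 2.

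**Working it through.** **1. The plan's own figure.** Inputs from 2.4.8: difference 0.3, SD 0.5, 85% power, alpha 0.05 (two-sided assumed). A paired t-test at n = 27 has noncentrality (0.3/0.5) × √27 = 3.118 and power 0.851, so the stated 27 reproduces. The calculation therefore treats the comparison as within-patient and holds no allowance for a period shift.

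**2. Is the contrast biased?** With one baseline B for both periods:
- absolute: (B − Y_pregabalin) − (B − Y_placebo) = Y_placebo − Y_pregabalin
- percent: (Y_placebo − Y_pregabalin)/B

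B drops out of the numerator. A uniform shift d between periods enters with opposite sign in the two sequences and averages to zero when they are balanced. With unequal numbers the residual is d × (n1 − n2)/n: for d = 1 SD of the within-patient difference, 1/27 = 0.04 SD at 14:13 and 5/35 = 0.14 SD at 20:15. In a simulation with assumed SDs, 28 patients, a 1-point shift and no true effect, the planned slope contrast averaged −0.04 and was rejected 5.0% of the time.

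**3. Cost of omitting a period term.** A shift of d SD multiplies the error variance by 1 + d². At n = 27, power falls from 0.85 to 0.83 (d = 0.25), 0.77 (d = 0.5) or 0.56 (d = 1).

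**4. Value of the covariate.** Let r be the correlation between the within-patient difference in pre-period scores and that in outcome, net of the period effect. The documents do not give it. With n = 28 and 26 df before adjustment, the variance factor is (1 − r²) × 25/24, where 25/24 is the cost of estimating the covariate. The noncentrality that gives 85% power at 26 df (3.113) is divided by the square root of this factor and tested at 25 df. Equivalent extra patients = 28/factor − 28.

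| r | Factor | Power | Extra patients |
|---|---|---|---|
| 0 | 1.042 | 83.4% | −1.1 |
| 0.2 | 1.000 | 84.9% | 0 |
| 0.3 | 0.948 | 86.7% | 1.5 |
| 0.4 | 0.875 | 89.2% | 4.0 |
| 0.5 | 0.781 | 92.3% | 7.8 |

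With a sequence term as well, the factor becomes (1 − r²) × 25/23 at 24 df: power is about 82% at r = 0 and 85% at r = 0.3, but no longer depends on d.

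**5. What r is plausible?** If pain drifts as a random walk observed at weeks 0, 4, 6 and 10, the pre-period difference spans weeks 0-6 and the outcome difference weeks 4-10. Each has variance 6 units and they share weeks 4-6, so r = 2/6 = 0.33. Measurement error lowers this, often below 0.2. Values of 0.4-0.5 need a persistent patient-specific trend.

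**6. Substituting Visit 3 as the period-2 baseline.** The variance factor is 1 + k² − 2rk, where k = SD of the baseline difference / SD of the outcome difference. This helps only if r > k/2. At k = 1 and n = 27, power is 0.56 (r = 0), 0.72 (r = 0.3) and 0.85 (r = 0.5).

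**7. Simulated SD of the slope contrast** (assumed inputs; the period columns also carry a period-by-MPT term, one more than proposed below):

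| Scenario | As planned | Period terms | Period terms + covariate | Visit 3 substituted |
|---|---|---|---|---|
| No uniform shift | 5.78 | 6.21 | 6.10 | 7.03 |
| 1-point uniform shift | 6.84 | 6.16 | 6.04 | 8.83 |
| Patient drift SD 1.5, precise Visit 3 score | 7.41 | 7.80 | 6.11 | 6.29 |

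A uniform shift is handled almost entirely by the period terms; large patient-specific drift is handled by the covariate.

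**The case against.** A reader might infer that crediting earlier change to the second treatment distorts the comparison of pregabalin with placebo. The documents do not support that: the baseline is common to both periods and sequence is randomised (2.4.1), so the shift falls on both treatments. What is left is extra variance, plus a small imbalance if completers differ by sequence.

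A reader might also infer that precision is certainly lost. That too goes beyond the documents, which give no r. With no period shift and r below about 0.2 the covariate costs a little power, and the no-shift row above shows the adjusted model doing worse.

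Percent relief from pain at entry is a legitimate definition of response; a patient who goes 6, 4, 3 does have half the entry pain. Nor does 2.2 contradict it: "analgesic response (% pain reduction) after 4-weeks of treatment with pregabalin vs. placebo" says when response is assessed, not from which score. So period-2 responder status is not wrong as defined; it simply includes change from before period 2.

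Visit 3 has weaknesses of its own. The entry requirement of pain above 3 does not apply there, so as a denominator it can be near or at zero. It follows the first treatment, so carry-over would contaminate it. These points stand, and they argue for a covariate rather than a new baseline.

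Finally, the lack of a role for Visit 3 is read from silence in 2.4.7 to 2.4.9, and Figure 1 was not available for this check. Even so, the baseline for each period and the content of the Visit 3 score should be stated.

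**Conclusion.** The point holds as an inexpensive improvement, not as a validity fault. Visit 1 is the only baseline, no analysis has a period term, and a scheduled off-drug score goes unused. The treatment contrast is not biased by this. An unmodelled period shift of 0.25 to 0.5 SD would take power from 0.85 to between 0.83 and 0.77. The covariate alone, at 28 completers, moves 85% to about 83% at r = 0, breaks even near r = 0.2 and gives about 87% at r = 0.3, worth some 1.5 patients. If there is no shift at all, the two terms together break even near r = 0.3.

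These sizes assume a within-patient slope comparison (the form that reproduces 27), balanced sequences, and ranges for r, k and d that the documents do not supply.

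**What to change.** In 2.4.7:

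1. State that Visit 1 is the baseline for the percent and absolute reductions in both periods.
2. Analyse the within-patient pregabalin-placebo difference with a period (sequence) term. For the primary outcome, regress that difference on Visit 1 MPT; the MPT coefficient is the difference in slopes.
3. Add as a covariate the score before the pregabalin period minus the score before the placebo period, from Visits 1 and 3. Use the outcome's scale: points for absolute reduction, points divided by the Visit 1 score for percent reduction.
4. State that the Visit 3 NRS asks for the same past-week average as Visit 1.
5. Recompute period-2 percent reduction and 50% response from Visit 3 as a sensitivity analysis only, with a stated rule for low or zero Visit 3 scores.
6. Keep Visit 1 MPT as the predictor, since the objective concerns baseline MPT.

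The visit and the score are already scheduled, so this is wording, settled before unblinding. The costs are one degree of freedom per added term (about 1.6 points of power for the covariate if r = 0, about 3 for both terms if neither explains anything) and reliance on no residual drug effect at Visit 3.

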	
 2. Spontaneous pain at baseline on 0-10 Numerical Rating Scale (NRS); 3. Assessment of pain symptoms on Neuropathic Pain Symptom Inventory (NPSI) and Brief Pain Inventory (BPI). 4. Assessment of mood on Depression, Anxiety and Positive Outlook Scale (DAPOS), and assessment of sleep on MOS Sleep Problem Index (SPI) scale. 5. Intraepidermal nerve fiber density and length of a 3-mm skin punch biopsy. 
Testing for intervention response (repetitive testing):
 
 1. Daily average and maximum pain intensity recording on 0-10 NRS; 2. Scoring of NPSI, BPI, DAPOS and SPI questionnaires at the end of week 4
Statistical Methodology	
The primary outcome is the comparison of slopes of the two correlations: baseline MPT vs % pain reduction with pregabalin, and baseline MPT vs % pain reduction with placebo. The two slopes will be compared using t-test. Significant difference between slopes will indicate that baseline MPT correlates with pregabalin response (vs. placebo response) in painful CIPN.
 
As secondary analyses, we will compare mean absolute pain reduction with pregabalin to absolute pain reduction to placebo (both for average daily pain and maximum daily pain), using paired t-test, given normal data distribution. If normal distribution is not obtained, we will use Wilcoxon signed ranked test.
 
In addition, we will perform Fisher exact test to compare the proportion of patients with 50% or more reduction in average pain intensity from baseline with pregabalin vs. placebo. Number needed to treat (NNT) will be calculated from this proportion of responders to pregabalin and placebo.

Table of Contents

1. SYNOPSIS	2
2. STUDY PROTOCOL	6
2.1 Background and Significance	6
2.2 Objective.....	8
2.3 Patient Selection	8
2.3.1 Inclusion Criteria	8
2.3.2 Exclusion Criteria	8
2.4 Design and Procedures.....	9
2.4.1 Study Design.....	9
2.4.2 Pre-Study Period	10
2.4.3 Study Period.....	11
2.4.4 Minimization of Bias	14
2.4.5 Observations and Measurements	15
2.4.6 QST protocol.....	15
2.4.7 Statistical Methods.....	17
2.4.8 Sample Size.....	18
2.4.9. Dealing with missing data.....	18
2.4.10 Clinical Procedures and Laboratory Tests	18
2.4.11 Drug procurement and storage.....	19
3.0 MANAGEMENT OF INTERCURRENT EVENTS	19
3.1 Adverse Experiences.....	19
3.2 Premature Discontinuation	21
3.3 Potential Risks	21
3.4 Procedures to Minimize Potential Risks.....	22

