2.4 Design and Procedures

2.4.1 Study Design

This is a prospective, randomized, double-blind, placebo-controlled, cross-over pilot study in 35 evaluable subjects with painful CIPN. If our hypothesis is confirmed, then patients with lower MPT at baseline will have larger analgesic effect with pregabalin than with placebo.

Registration, Randomization, and Blinding

Subjects that meet all criteria and wish to participate will be assigned study ID # and be randomized for the sequence of treatment for the study sessions. Patients may not start any protocol intervention until registration through the Siteman Cancer Center (SCC) is complete. The following steps will be taken before any study interventions occur: 1) confirmation of patient eligibility, 2) registration of patient in the SCC database, and 3) assignment of study ID #.

According to a computer-generated list of randomization numbers, the sequence of interventions will be determined: pregabalin and then matching placebo, or vice versa. Randomization will be performed by blocks of 8 subjects, without stratification. An unblinded

investigator will be assigned to match the study number with randomized treatment sequence, and this person will dispense the study medications. This investigator will not be involved at any stage at patient assessment, data collection or analysis. The participants and all other study personnel will be blinded to the treatment sequence allocation. At the end of the study, the subjects will be asked to complete a participant blinding questionnaire, to assess the risk of possible unmasking. As an additional approach to identify inadvertent failure in randomization or patient allocation, a single blood sample will be obtained at the last visit of each session, to determine the presence of pregabalin in plasma in patients allocated to pregabalin, and lack of drug in the placebo arm.

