2.4.5 Observations and Measurements

2.4.5.1 Primary Outcome Measures

Primary outcome:

Correlation between MPT at baseline and reduction in spontaneous pain intensity (% reduction on 0-10 NRS) at the end of 4-week treatment. The slopes of the correlation obtained from pregabalin vs. placebo will be compared.

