2.4.8 Sample Size

The sample size calculation was performed for detecting a significant difference between correlations on % pain reduction vs. MPT slopes of pregabalin and placebo in linear bivariate regression. Assuming slope and SD data based on our preliminary results of MPT vs. response with another drug, lidocaine (Haroutiunian, Nikolajsen et al. 2013); to detect 0.3 (SD=0.5) difference in correlation coefficients between the two slopes, with 85% power and alpha=0.05, 27 participant are required in this cross-over design. We will aim to recruit 35 patients to account for possible 20% dropout rate.

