2.4.9. Dealing with missing data

If less than 10% data on primary outcomes are missing, we will perform our primary analysis per protocol, and perform sensitivity analysis using intent to treat (ITT) approach, where missing pain intensity data will be imputed using last observation carried forward (LOCF) method. If more than 10% primary outcomes data are missing, we will use mixed-effects model imputation method [full information maximum likelihood (Little, D'Agostino et al. 2012)], which considers the reasons for missingness, and is more appropriate for reducing bias.

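### The primary slope comparison is an unqualified t-test; the plan does not say that it uses the pairing of both slopes within patients

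*Combined protocol and SAP*

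**What the plan says.** Section 2.4.7 specifies the primary test as "The two slopes will be compared using t-test", and the synopsis has the same wording: "The two slopes will be compared using t-test. Significant difference between slopes will indicate that baseline MPT correlates with pregabalin response". Section 2.4.5.1 says only "The slopes of the correlation obtained from pregabalin vs. placebo will be compared". The response is the percent reduction from baseline to the mean of days 24-28 of each treatment phase.

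Section 2.4.8 adds that the setting is a linear bivariate regression, that alpha is 0.05, and that the trial is sized "to detect 0.3 (SD=0.5) difference in correlation coefficients between the two slopes", from which "27 participant are required in this cross-over design". Section 2.4.1 describes a "cross-over pilot study in 35 evaluable subjects with painful CIPN".

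Pairing is named once in 2.4.7, for the secondary comparison of mean absolute pain reduction: "using paired t-test, given normal data distribution". Section 2.4.9 brings in a within-patient type of method under one condition: "If more than 10% primary outcomes data are missing, we will use mixed-effects model imputation method". It names no model terms, no covariance structure and no test of the slopes.

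**The concern.** A t-test of two regression slopes has a standard textbook form: fit two regressions, then divide the slope difference by the root of the summed squared standard errors. That form assumes independent samples. Here each completer contributes one point to each regression at the same MPT value. If the pre-study baseline of section 2.4.2 serves both periods, the two percent reductions also share a baseline pain score. The two slope estimates are therefore correlated, and the textbook standard error leaves the correlation out.

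Two analysts following 2.4.7 could report different p-values and intervals from the same data on the only primary question. If the textbook form were used and rho were positive, a null result might reflect the test rather than the data. Section 2.4.4 gives reduced inter-subject variability as the reason for the cross-over, and this form would give up that gain for the primary test.

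**Working it through.** **Inputs.** From 2.4.8: difference 0.3, SD 0.5, 85% power, alpha 0.05 (sidedness not stated; two-sided taken here), 27 required, 35 recruited for 20% dropout. From 2.4.1: cross-over, 35 evaluable. Not in the documents: the SD of MPT, and rho, the correlation between a patient's two residuals given MPT. A range of rho is shown.

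**Step 1: the plan's own figure.** Take 0.3/0.5 = 0.6 as a two-sided paired t-test of a mean difference, with noncentrality 0.6√n. Power is 0.836-0.837 at n = 26 and 0.851 at n = 27, so 27 is reproduced exactly. An independent two-group test of means at 0.6 needs about 51 per group (power 0.851); 27 per group gives 0.58. The match points to pairing. It is a match to a test of means, however, and the requirement for a slope test also depends on the SD of MPT.

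**Step 2: the omitted term.** Let both regressions use the same n patients and the same MPT values, with sum of squares Sxx and residual SDs s1 and s2.

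- Correct: Var(b1 − b2) = (s1² + s2² − 2·rho·s1·s2)/Sxx
- Ordinary two-slope form: (s1² + s2²)/Sxx

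With equal SDs, the ordinary standard error is too large by 1/√(1 − rho), which is 1.20, 1.41 and 1.83 at rho 0.3, 0.5 and 0.7.

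**Step 3: effect on the test.** This was simulated with MPT held fixed (sample SD 1) and unit residual SDs. The slope difference is set so that the paired regression on n − 2 df has 85% power at n = 27. The ordinary form uses 2n − 4 df. The n = 28 column is 35 × 0.8.

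| rho | slope difference | ordinary form: true alpha, n = 27 | ordinary power, n = 27 | n = 28 | n = 35 |
|---|---|---|---|---|---|
| 0.3 | 0.724 | 0.02 | 0.76 | 0.78 | 0.88 |
| 0.5 | 0.612 | 0.007 | 0.61 | 0.63 | 0.77 |
| 0.7 | 0.474 | 0.001 | 0.32 | 0.34 | 0.48 |
| paired test, any rho | as above | 0.05 | 0.85 | 0.86 | 0.93 |

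The n = 35 figures are good to about 0.01. At rho 0.2 the loss is small (about 0.80 at n = 27 and 0.91 at n = 35), and at rho 0 there is none.

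MPT is in fact measured, not fixed. With MPT drawn at random and the effect held at 0.6 SD of the within-patient difference, power at n = 27 is about 0.72, 0.57 and 0.30, against 0.81 paired. The level falls for both tests, and the gap stays much the same.

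**Step 4: would 2.4.9 take over?** A 20% dropout is 7 of 35 patients. Each loses one or two of the 70 period outcomes, so 7/70 = 10% to 14/70 = 20% are missing. The plan's own dropout assumption could therefore trigger the mixed-effects route.

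**The case against.** The plan never states an independent-samples test. The words can equally describe the t-test of a treatment-by-MPT coefficient. Section 2.4.8 speaks of regression and of the cross-over, and its 27 matches a paired calculation. With planned dropout, 2.4.9 may lead to a likelihood method that ordinarily models within-patient correlation. With 35 evaluable patients even the ordinary form keeps 0.88 power at rho 0.3, above the planned 85%. The trial is also called a pilot. All of this stands, and it limits the weight of the point. None of it states how the slopes are to be tested: the sizing match is to a mean difference, and 2.4.9 is a conditional imputation rule without a slope test.

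Three stronger readings are tempting, and the documents do not support them.

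- **A wrong test has been chosen.** A reader might infer this from the contrast with the paired test for means, or from Fisher's exact test for the responders. The contrast shows an omission, not a choice. The responder test is a separate secondary matter.
- **False positives are inflated.** That needs negative rho; at rho −0.2 the true alpha would be about 0.074. The documents give no sign for rho, and a shared baseline score makes positive rho the more natural expectation. The error is then conservative.
- **The sample size is wrong.** Nothing here shows that, and 27 agrees with a paired intention.

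**Conclusion.** The omission is certain: no section says that the primary slope test accounts for the same patients supplying both slopes. The consequence is conditional on two things that the documents leave open, namely that the ordinary form is programmed and that rho is materially above zero. If both hold, the harm is lost power and intervals that are too wide. At 27 patients the loss runs from about 0.09 at rho 0.3 (0.85 − 0.76) to about 0.53 at rho 0.7 (0.85 − 0.32). At 35 it runs from about 0.05 to 0.45 (0.93 − 0.88 and 0.93 − 0.48). These figures assume equal residual SDs, complete pairs and fixed MPT. The slope estimates are unaffected. The text should be corrected before analysis, because choosing the form after unblinding would be a post hoc choice on the primary question.

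**What to change.** In 2.4.7 and the synopsis, replace the sentence on the t-test with:

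> For each patient, the pregabalin-minus-placebo difference in percent pain reduction is regressed on baseline MPT, with treatment sequence as covariate. The primary test is the two-sided t-test of the MPT coefficient on n − 3 degrees of freedom.

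The MPT coefficient is the difference between the two slopes, so the estimand is the same. The paired regression held alpha at about 0.05 at every rho tried. The sequence term absorbs a period effect.

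The difference regression drops patients with only one period. For the case in 2.4.9 of more than 10% missing data, state the matching mixed model instead: treatment, period, sequence, MPT and treatment-by-MPT, with unstructured within-patient covariance and small-sample degrees of freedom. Treatment-by-MPT is the tested term. Patients with one period then still contribute.

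The cost is a few lines of text and code. The sequence covariate takes about 0.01-0.02 of power (0.85 to 0.83-0.84 at n = 27). Visits, data collection, section 2.4.8 and recruitment stay as they are.
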